9. MEASUREMENT OF EFFECT

9.1 Definitions

Evaluable for toxicity. All subjects are evaluable for toxicity after receiving first dose of study treatment.

Evaluable for objective response. All patients who have received at least one dose of study drug at any time during the study will be considered evaluable for response, with the exception of patients that withdraw consent prior to disease re-evaluation. Patients who withdraw consent before disease re-evaluation may be replaced. Patients who come off study prior to disease re-evaluation with imaging due to clinical deterioration will be coded as progressing. Response criteria will be classified by RECIST 1.1 criteria (**Appendix E**)

9.2 Methods for Evaluation of Measurable Disease

Imaging should include the chest, abdomen, and pelvis. Tumor imaging is strongly preferred to be acquired by computed tomography (CT). For the abdomen and pelvis, contrast-enhanced magnetic resonance imaging (MRI) may be used when CT with iodinated contrast is contraindicated, or when local practice mandates it. The same imaging technique regarding modality, ideally the same scanner, and the use of contrast should be used in a participant throughout the study to optimize the reproducibility of the assessment of existing and new tumor burden and improve the accuracy of the assessment of response or progression based on imaging. Body scans should be performed with breath-hold scanning techniques, if possible.

All baseline evaluations should be performed as closely as possible to the beginning of treatment and no more than 28 days before the beginning of the treatment. The site study team must review screening images to confirm the participant has measurable disease per RECIST 1.1. Subjects will be evaluated for anti-tumor effect by follow-up imaging as outlined in the study calendar. All subsequent scans (post-treatment) will be compared to the same pretreatment scan that was used prior to initiating of study treatment.

All measurements should be taken and recorded in metric notation using a ruler or calipers.

The definition of measurability of lesions on CT scan is based on the assumption that CT slice thickness is 5 mm or less. If CT scans have slice thickness greater than 5 mm, the minimum size for a measurable lesion should be twice the slice thickness.

10. DATA REPORTING / REGULATORY REQUIREMENTS

Adverse event guidelines and instructions for AE reporting can be found in **Section 5**.

[name] will hold the IND for this study. She will comply with all regulated reporting requirements to the FDA.

10.1 Data Management

All information will be collected on study-specific case report forms (CRFs) by study staff. These data will be reviewed for completeness and accuracy by the Principal Investigator at each site.

Protocol Chair

The Protocol Chair and/or designee is responsible for performing the following tasks:

- Coordinating, developing, submitting, and obtaining approval for the protocol as well as its subsequent amendments.
- Assuring that all participating institutions are using the correct version of the protocol.
- Taking responsibility for the overall conduct of the study at all participating institutions and for monitoring the progress of the study.
- Reviewing and ensuring reporting of SAE
- Reviewing data from all sites.

Coordinating Center (Johns Hopkins University)

The Coordinating Center (or its representative) is responsible for performing the following tasks:

- Ensuring that IRB approval has been obtained at each participating site prior to the first subject registration at that site, and maintaining copies of IRB approvals from each site.
- Monitoring subject registration.
- Collecting and compiling data from each site.
- Establishing procedures for documentation, reporting, and submitting of AE's and SAE's to the Protocol Chair, and all applicable parties.
- Facilitating audits by securing selected source documents and research records from participating sites for audit, or by auditing at participating sites.

Participating Sites

Participating sites are responsible for performing the following tasks:

- Following the protocol as written, and the guidelines of Good Clinical Practice (GCP).
- Submitting data to the Coordinating Center.
- Consent subjects promptly and enroll eligible subjects in EDC.
- Providing sufficient experienced clinical and administrative staff and adequate facilities and equipment to conduct a collaborative trial according to the protocol.
- Maintaining regulatory binders on site and providing copies of all required documents to the Coordinating Center.
- Collecting and submitting data according to the schedule specified by the protocol.

10.2 Safety Meetings

Scheduled meetings will occur on a regular basis with the frequency dependent on the rate of subject accrual and the progress of the study. Meetings will include the protocol principal investigator, study coordinator(s), data manager(s), lead research nurses(s), sub-investigators (as appropriate), collaborators (as appropriate), and biostatisticians (as appropriate) involved with the conduct of the protocol. During these meetings matters related to the following will

be discussed: safety of protocol participants, validity and integrity of the data, enrollment rate relative to expectation, characteristics of participants, retention of participants, adherence to protocol (potential or real protocol violations), data completeness, and progress of data for objectives.

Monthly teleconferences will be scheduled to include the Coordinating Center and the clinical trial sites. During these meetings, the Coordinating Center and clinical trial sites shall discuss the following: study protocol updates, safety data, enrollment status, and progress of data for objectives.

10.3 Monitoring

Eligibility for all sites will be monitored by the Protocol Chair. The protocol will be monitored internally by the Principal Investigator at each site. Data monitoring of this protocol will occur on a regular basis with the frequency dependent on the rate of subject accrual and the progress of the study. External monitoring will occur according to the following guidelines:

Johns Hopkins SKCCC: The SKCCC Compliance Monitoring Program will provide external monitoring for JHU-affiliated sites in accordance with SKCCC DSMP (Version 6.0, 02/21/2019). The SMC Subcommittee will determine the level of patient safety risk and level/frequency of monitoring.

Participating site(s): The protocol will be monitored at each participating site by a member of the Johns Hopkins study team regulatory staff. A report of the reviews will be submitted to the Johns Hopkins principal investigator and SKCCC CRO.

11. STATISTICAL CONSIDERATIONS

11.1 Sample Size

Phase I will be enrolled in a standard 3+3 design with up to 18 patients. For the purposes of dose finding, DLTs will be evaluated during the first cycle for each patient. An initial cohort of 3 patients will be enrolled. If 0-1/3 have a DLT then 3 additional patients will be enrolled at the same dose level. If 2-3/3 DLTs are observed, then the dose will be considered too toxic and the next lower dose level will be enrolled. The RP2D is the dose at which $\leq 1/6$ patients have a DLT (i.e. if 0/3 of the initial patients have a DLT then an additional 3 will be recruited at the highest feasible dose to establish the RP2D).

During Phase II 42 patients will be recruited: 21 patients with colorectal cancer with PIK3CA mutation (cohort A) and 21 with WT PIK3CA with known lack of sensitivity to immune checkpoint inhibitor therapy (cohort B). ORR (CR+PR) at 6 months the primary endpoint and will be evaluated separately in each cohort. Enrollment will be carried out in 2 stages so that the study can terminate early if the combination of copanlisib and nivolumab is not sufficiently effective. A design similar to Simon's minimax design with relaxed futility stopping will be employed to test the null hypothesis that the true ORR is 5% or less.³⁰⁻³¹ In the first stage, 12 subjects will be accrued in each cohort. If there are no responders among the first 12 patients, the study will be terminated for futility. Otherwise, 9 additional patients will be accrued for a

total of 21 treated subjects. Patients who withdraw consent before disease re-evaluation will not be considered evaluable for response and may be replaced. Patients who come off of study prior to disease re-evaluation with imaging due to clinical deterioration will be considered evaluable for response and will be coded as progressing. If ≥ 3 out of the 21 patients have a response, then the trial will be considered a success for that cohort. If the true response rate is 20% (alternative hypothesis rate), then the probability of a declaring the treatment a success is 0.80 (power). If the true response rate is 5% (null hypothesis rate), then the probability of declaring the treatment a success is 0.08 (type I error).

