1. OBJECTIVES

1.1 Primary Objectives

1. Phase I: To determine the recommended phase II dose (RP2D) of copanlisib with fixed dose nivolumab
2. Phase II/Clinical: To determine 6-month objective response rate (ORR) of patients treated with copanlisib and nivolumab and compare the ORR of patients in Cohort A (MSS colorectal cancer patients with PIK3CA mutations) and Cohort B (MSS colorectal cancer patients with WT PIK3CA)

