1.5 Study Design

This is a multi-center, open-label, Phase I/II study. Phase 1 consists of a 3+3 dose de-escalation design to determine the dose of copanlisib for use in combination with nivolumab. Approximately 6-18 subjects with solid tumors will be treated in Phase I and will be monitored for dose limiting toxicities (DLTs) through their first cycle of treatment. Complete information on the definition of DLTs and dose de-escalation rules can be found in **Section 4.3**.

The Phase II portion of the study will evaluate the safety and clinical activity of copanlisib and nivolumab in two cohorts of patients with previously treated metastatic colon cancer. Cohort A will enroll patients with PI3K mutation and Cohort B will enroll patients with wildtype PI3K status. Twenty-one patients are targeted for enrollment in each cohort, for an approximate total of 42 patients in Phase II. Enrollment in Phase II will be initiated once the recommended phase II dose (RP2D) has been determined in Phase I.

For all patients, the study will consist of a screening period, a treatment period, and a follow-up period. Screening evaluations will be done within 28 days prior to the start of study treatment.

Each treatment cycle is 28 days. Patients in both Phase I and Phase II will receive nivolumab on Day 1 of each cycle (every 4 weeks) and copanlisib on either Day 1, Day 8, and Day 15 of each cycle (3 week on, one week off) or on Day 1 and 15 of each cycle (every 2 weeks), depending on the dose level and RP2D. Complete information on study drug administration, schedule, and dosing can be found in **Section 4.2**.

Phase II enrollment will be carried out in 2 stages so that the study can terminate early if the combination of copanlisib and nivolumab is not sufficiently effective. In the first stage, 12 subjects will be accrued to each cohort. If there are no responders among the first 12 patients, the study will be terminated for futility. Otherwise, 9 additional patients will be accrued for a total of 21 treated subjects. If ≥ 3 out of the 21 patients have a response, then the trial will be considered a success for that cohort.

Clinical and immune responses will be evaluated at baseline and during treatment through tumor assessments, biopsies, and PBMC and plasma collection. Tumor assessments will be made using RECIST 1.1.

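### The futility rule ends the whole study at 0/12, but accrual, evaluation, success and the stated power and type I error are all per cohort

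*Combined protocol and SAP*

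**What the plan says.** Phase II enrols two cohorts of 21: A (PIK3CA mutation) and B (PIK3CA wild type). The two-stage rule appears in Section 1.5 (Study Design) and again in Section 11.1 (Sample Size).

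- **Stage 1:** "In the first stage, 12 subjects will be accrued in each cohort" (11.1; nearly identical in 1.5).
- **Futility:** "If there are no responders among the first 12 patients, the study will be terminated for futility" (same words in both sections).
- **Stage 2:** "Otherwise, 9 additional patients will be accrued for a total of 21 treated subjects" (1.5; repeated in 11.1).
- **Success:** "If ≥ 3 out of the 21 patients have a response, then the trial will be considered a success for that cohort" (11.1; repeated in 1.5).

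Section 11.1 also says that ORR is assessed in each cohort on its own. It gives power 0.80 at a true ORR of 20% and type I error 0.08 at 5%. Section 1.1 makes a between-cohort contrast part of the primary Phase II objective: "compare the ORR of patients in Cohort A (MSS colorectal cancer patients with PIK3CA mutations) and Cohort B".

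**The concern.** The success sentence is tied to a cohort and the futility sentence is not. Taken at its word, a cohort with no responders in its first 12 patients ends the study, including a cohort that is responding. No available text says that the other cohort continues.

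The plan has to handle this case. Its primary objective compares the two cohorts' response rates, so it allows for them to differ, and a split at stage 1 is then likely. Without a clear rule, whether the responding cohort continues would be decided in an open-label trial after the responses are known. That decision determines whether an active cohort completes its 21 patients and whether the A-versus-B comparison can be made at the planned size.

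**Working it through.** **Inputs from Section 11.1:** null ORR 5%; alternative ORR 20%; stage 1 n = 12, stop at 0 responders; stage 2 n = 9; success at 3 or more of 21.

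**Assumptions:** the cohorts are independent. The other cohort's ORR is set to 5% and 20% (the plan's own rates) and to 10% (an assumed value between them). Relative accrual is not given in the documents.

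**Step 1. Reproduce the stated figures with a per-cohort stop.**

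P(success) = P(Bin(21, p) ≥ 3) − P(0/12) × P(Bin(9, p) ≥ 3), where P(0/12) = (1 − p)^12.

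- p = 20%: P(0/12) = 0.80^12 = 0.0687. The subtracted term is 0.0687 × 0.2618 = 0.0180. Power = 0.8213 − 0.0180 = **0.8033**.
- p = 5%: P(0/12) = 0.95^12 = 0.5404. The subtracted term is 0.5404 × 0.0084 = 0.0045. Type I error = 0.0849 − 0.0045 = **0.0804**.

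These are the plan's 0.80 and 0.08. The other cohort does not enter the formula.

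**Step 2. Either cohort at 0/12 closes both, with closure counted as no success.** Multiply the per-cohort figure by 1 − (1 − p_other)^12. For p_other = 5%, 10% and 20% the factor is 1 − 0.5404 = 0.4596, 1 − 0.2824 = 0.7176 and 1 − 0.0687 = 0.9313.

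**Step 3. The study stops only when both cohorts are at 0/12.** The subtracted term from step 1 is multiplied by (1 − p_other)^12. For example, with p_other = 5%, power = 0.8213 − 0.0180 × 0.5404 = 0.8116.

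Each cell gives power at ORR 20%, then type I error at ORR 5%:

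| Other cohort's ORR | Per-cohort stop | Either at 0/12 closes both | Both must be at 0/12 |
|---|---|---|---|
| 5% | 0.803; 0.080 | 0.369; 0.037 | 0.812; 0.0825 |
| 10% | 0.803; 0.080 | 0.576; 0.058 | 0.816; 0.0836 |
| 20% | 0.803; 0.080 | 0.748; 0.075 | 0.820; 0.0846 |

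A simulation of step 2 with 200,000 replicates gave power 0.369 and 0.748 for an other-cohort ORR of 5% and 20%.

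**Step 4. Dependence on accrual.** Step 2 is the worst case. If the active cohort has 12 patients when the study closes, and 3 or more responders among them still count as success, P(0/12 in the other cohort) × P(Bin(12, 20%) ≥ 3) is added. For an other-cohort ORR of 5% that is 0.369 + 0.5404 × 0.4417 = 0.608; for 10% and 20% the results are 0.701 and 0.778. If the active cohort has already reached 21, nothing is lost and power is 0.803.

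**Step 5. How often the cohorts split.** P(exactly one at 0/12) = a(1 − b) + b(1 − a), where a and b are the two cohorts' probabilities of 0/12.

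- 20% and 5%: 0.0687 × 0.4596 + 0.5404 × 0.9313 = 0.032 + 0.503 = 0.535.
- 20% and 10%: 0.0687 × 0.7176 + 0.2824 × 0.9313 = 0.049 + 0.263 = 0.312.
- 20% and 20%: 2 × 0.0687 × 0.9313 = 0.128.

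In the first two lines the second term (0.50 and 0.26) is the case that matters most: the 20% cohort has passed stage 1 and the other has not.

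**The case against.** The best defence is that the intent is plain from the context. The sentence before the rule sets 12 patients per cohort. The alternative branch of the same rule leads to 21, one cohort's size, where a study-wide rule would lead to 42. The success sentence itself uses the word trial for a cohort-level result, and the stated 0.80 and 0.08 come from a per-cohort stop. Section 11.4 is equally loose: its toxicity trigger is counted per cohort, yet the consequence it names is reassessment of the trial. On this view the defect is editorial.

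The low power figures can also be challenged. The text does not say that either cohort at 0/12 closes both. A study-level rule requiring 0/12 in both loses no power, and its type I error still rounds to 0.08. The 0.37 needs the other cohort to be at 5% and closure always to count as failure.

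Most of this stands. The word study is probably loose usage, the arithmetic in Section 11.1 is right, and 0.37 is a worst case. But a stopping rule is an instruction to be followed, and study-level language also appears in the stated purpose of the two stages. Section 11.4 shows the same mixture of levels, so it does not settle the matter. The figures in Section 1.5 are not shown in the available text and could not be checked; even if they are clear, the sentence in both sections would still need to agree with them.

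**Conclusion.** The concern holds. The futility sentence does not match the per-cohort design around it. Only an independent stop in each cohort gives the stated power and type I error regardless of the other cohort's response rate or accrual. If 0/12 in either cohort closed both, power at ORR 20% could fall from 0.80 to between 0.37 and 0.75 for an other-cohort ORR between 5% and 20%, with the loss shrinking to none as the active cohort nears 21 patients. If both cohorts had to be at 0/12, the figures would stay close to those stated (power 0.81 to 0.82). These results rest on independent cohorts and the assumed response rates in the other cohort. The design is sound; the written rule should be corrected before it has to be applied.

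**What to change.** In Sections 1.5 and 11.1, replace the futility sentence with one to this effect: *a cohort with no responder among its first 12 patients stops for futility, and the other cohort carries on under its own rule.* This changes one sentence in two places. Sample size, decision thresholds, power 0.80 and type I error 0.08 are unchanged.

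If a study-wide stop is intended, state whether it is triggered by 0/12 in either cohort or only in both, say how a cohort closed before 21 patients is to be judged, and restate the power and type I error for that rule.

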4.5 Duration of Therapy and Criteria for Removal from Study Treatment

In the absence of treatment delays due to adverse event(s), treatment may continue indefinitely until one of the following criteria applies. The reason for study treatment removal and the date the patient was removed must be documented in the Case Report Form.

A participant must be discontinued from study treatment but continue to be monitored in the study follow-up for any of the following reasons:

- The participant or participant's legally acceptable representative requests to discontinue study treatment
- Confirmed radiographic disease progression outlined in **Section 9** and **Appendix E**
 - As immunotherapy has been shown to cause pseudo-progression, patients are eligible to remain on study after progression if they are clinically stable, if they desire and their treating physician agrees it is in the interest of the patient. If subsequent imaging confirms progression, the patient's date of progression will be the date of first progression
- Clinical progression or deterioration

- Progression or recurrence of any malignancy, or any occurrence of another malignancy that requires active treatment
- Unacceptable adverse experiences as described in **Section 4.4.2** Exceptions must be approved by the IND Sponsor.
- The participant has a medical condition or personal circumstance which, in the opinion of the investigator and/or sponsor, placed the participant at unnecessary risk from continued administration of study treatment.
- Investigator's decision to withdraw the subject
- The participant has a confirmed positive serum pregnancy test
- Noncompliance with study treatment or procedure requirements

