10. HDL, LDL, triglycerides, total cholesterol; performed at Screen and Day 1 of every other cycle (starting at Cycle 2)
11. If TSH is abnormal, T3 and FT4 will be assessed.
12. Patients with positive tests for HBsAg or HIV are excluded from study. Patients with positive test for anti-HCV antibody will be eligible if they are negative for HCV-RNA. These patients should perform HCV RNA test with PCR monthly through treatment and 6 months thereafter. If viral load becomes positive, patient should be withdrawn from the study.
13. CMV PCR may be done up to 7 days prior to each Day 1 visit. CMV PCR should be done with

every cycle through cycle 6, then every 3 cycles thereafter.

14. Serum or urine pregnancy test required for WOCBP only. If urine pregnancy results cannot be confirmed as negative, a serum pregnancy test is required.
15. Bilirubin, hemoglobin, glucose, ketones, leukocytes, nitrite, pH, color, protein, RBC and WBC count, and specific gravity. Performed at baseline and Day 1 of every other cycle (starting at cycle2).
16. Labs and research blood should be collected within a window of 3 days prior to dosing. Labs may be repeated prior to dosing if needed.
17. MUGA scan or echocardiogram to measure LVEF; the method chosen at baseline must be the same throughout the whole study period (baseline and EOT); at EOT visit must be done if not previously done within 4 weeks.
18. Radiologic evaluations and tumor measurements will be performed at baseline (within 28 days of dosing), prior to each odd cycle (up to 1 week prior), and at End of Treatment visit. If patient comes off study for reasons other than disease progression, subject may have additional radiologic evaluations every 8 weeks until progression or start of new anti-cancer therapy. CT of the chest/abdomen/pelvis with contrast will be used, however, non-contrast CT chest and MRI abdomen/pelvis will be done for patients with contrast allergies.
19. Biopsy to be collected at baseline and 6 weeks after first dose of study drug (\pm 3 days, but before Cycle 2 Day 15 study drug). An optional biopsy may be performed at the time of progression. Approximately 6 core biopsy specimens will be obtained at each biopsy. Tumor biopsy will not be performed if the tumor is not accessible or if biopsy is considered not in the patient's best interest.

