11.2 Statistical Analyses

Data will be summarized descriptively within each phase overall and by subgroups of interest (e.g. cohort). The descriptive summary including demographics and baseline variables will include counts and percentages for categorical variables and means, medians, standard deviations, and quartiles for continuous variables.

ORR at 6 months, the primary outcome for Phase II, will be summarized using counts and percentages. Logistic regression will be used to compare the ORR between the two cohorts as well as to identify risk factors associated with ORR. Other binary outcomes (e.g. disease control at 6 months (SD+PR+CR) and immunologic response) will be analyzed using the same methods.

Time to event outcomes include overall survival (OS) and progression free survival (PFS). Overall survival is defined as the time from the first dose until death. Individuals without an event will be censored at the date of last contact. Progression free survival is defined as the time from the first dose until progression or death. Individuals who die will be counted as having progressed. Individuals without an event will be censored at the date of the last evaluation for progression. Kaplan-Meier curves will be used to graphically summarize the survival function and to estimate the median time to event and the proportion event-free at key intervals (e.g. 6 months) along with 95% confidence intervals. Cox proportional hazards models will be used to compare Cohorts A and B and to identify risk factors associated with OS and PFS. Graphical techniques (e.g. log-log plots) and formal statistical testing (e.g. Schoenfeld tests) will be used to assess the proportional hazards assumption. If necessary, alternate models (e.g. incorporating a time variable) will be considered.

Safety will be monitored continuously throughout the study, including the phase II component. Weekly team meetings and a minimum of monthly investigator calls will be conducted to review ongoing and resolved toxicity.

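### Does leaving out, and only optionally replacing, patients who withdraw consent before the first scan undermine the 3-of-21 decision rule?

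*Combined protocol and SAP*

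**What the plan says.** Section 1.5 describes the second stage as "9 additional patients will be accrued for a total of 21 treated subjects", and gives the enrolment target as "Twenty-one patients are targeted for enrollment in each cohort, for an approximate total of 42 patients in Phase II". Section 11.1 repeats the accrual wording. The design is meant to "test the null hypothesis that the true ORR is 5% or less", against an alternative of 20%. A cohort stops if none of the first 12 respond and succeeds if at least 3 of 21 do.

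Between the accrual sentence and the success rule, Section 11.1 inserts the evaluability rule: "Patients who withdraw consent before disease re-evaluation will not be considered evaluable for response and may be replaced". Section 9.1 agrees. Everyone with at least one dose is evaluable for response, "with the exception of patients that withdraw consent prior to disease re-evaluation", and those patients may be replaced. Both sections keep a patient who leaves before imaging because of clinical deterioration, coded as progressing.

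Section 11.2 says "ORR at 6 months, the primary outcome for Phase II, will be summarized using counts and percentages", without naming the analysis set.

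**The concern.** The accrual target is in treated patients, while the response set is smaller and replacement is optional. A dosed patient who withdraws in week 5 is one of the 21 treated but is not counted for response. Without replacement the rule is applied to 20 patients; with replacement 22 are treated. Both follow the text.

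The plan does not say when replacement happens, what 0 of 12 or 3 of 21 means if fewer are evaluable, or whether 5% and 20% are rates among treated or evaluable patients. It plans no response rate in all treated patients. In an open-label, uncontrolled cohort decided by three responders, a choice made after treatment starts could seem to let the decision be steered, and would make the stated error rates a range.

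**Working it through.** **Inputs.** From Section 11.1: 12 then 21 patients, stop at 0 of 12, success at 3 or more of 21, null 5%, alternative 20%. The withdrawal rate w is not in the documents; 2%, 5% and 10% are assumed.

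**Stated design.** P(success) = sum over x = 1 to 12 of P(Bin(12, p) = x) × P(Bin(9, p) ≥ 3 − x). Products below use unrounded factors.

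- p = 0.05: 0.3413 × 0.0712 + 0.0988 × 0.3698 + 0.0196 = 0.0243 + 0.0365 + 0.0196 = 0.0804.
- p = 0.20: 0.2062 × 0.5638 + 0.2835 × 0.8658 + 0.4417 = 0.1162 + 0.2454 + 0.4417 = 0.8033.

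Both match the plan's 0.08 and 0.80.

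**Who can be excluded.** Scans are scheduled "prior to each odd cycle (up to 1 week prior), and at End of Treatment visit" (Section 8.2). The first on-treatment scan therefore precedes Cycle 3, which starts after 2 × 28 = 56 days, so the exclusion window is about 7 to 8 weeks. Section 4.5 keeps patients who only stop treatment: "A participant must be discontinued from study treatment but continue to be monitored in the study follow-up". Only full withdrawal of consent in that window removes a patient.

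**Reading A: 5% and 20% are rates among evaluable patients.** With full replacement, exactly 12 and then 21 are counted, giving 0.0804 and 0.8033 at any w. Without replacement, and with withdrawal unrelated to response, a treated patient counts as a responder with probability p(1 − w):

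| w | Null rate | Type I error | Alternative rate | Power |
|---|---|---|---|---|
| 2% | 0.049 | 0.0767 | 0.196 | 0.7912 |
| 5% | 0.0475 | 0.0712 | 0.190 | 0.7719 |
| 10% | 0.045 | 0.0626 | 0.180 | 0.7369 |

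With a fixed number of unreplaced losses:

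| Evaluable at stage 1, then final | Type I error | Power |
|---|---|---|
| 12, 20 | 0.0724 | 0.7800 |
| 11, 20 | 0.0707 | 0.7714 |
| 12, 19 | 0.0645 | 0.7529 |
| 11, 19 | 0.0633 | 0.7457 |
| 10, 19 | 0.0615 | 0.7350 |

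**Selective replacement under Reading A.** Suppose withdrawals are replaced only when responders are short. The patients counted are still the first k evaluable ones, with k at most 21. Three responders among the first k are also three among the first 21, and a cohort that passed stage 1 with fewer than 12 evaluable has a responder among its first 12. Every success on the selective path is thus a success under full replacement, and type I error cannot exceed 0.0804. A simulation of 400,000 runs gave 0.0806 (w = 5%) and 0.0809 (w = 10%), Monte Carlo standard error 0.0004, consistent with that bound.

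**Reading B: 5% is the rate among all treated patients.** Without replacement, if withdrawers never respond, type I error is 0.0804. With full replacement:

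| w | Withdrawers never respond: 0.05/(1 − w) | Withdrawers respond at half the evaluable rate: 0.05/(1 − w/2) |
|---|---|---|
| 2% | 0.0843 | not tabulated |
| 5% | 0.0906 | 0.0853 |
| 10% | 0.1025 | 0.0906 |

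**Reported rate at the boundary, one withdrawal.** Not replaced: 3/20 = 15.0% evaluable against 3/21 = 14.3% treated. Replaced: 3/21 = 14.3% against 3/22 = 13.6%. The gap is about 0.7 points either way.

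**Cost of tightening the rule.** Counting the first 21 treated, with withdrawals as non-responders, gives the no-replacement row of Reading A: power 0.772 at 5% withdrawal, 0.737 at 10%. Mandatory replacement keeps 0.080 and 0.803 but needs on average 21/0.95 = 22.1 or 21/0.90 = 23.3 treated patients per cohort.

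**The case for a change.** The strongest case for a change is that the population is prespecified but the replacement decision is not, and that the remedy is cheap: a few words in three sections and one line in a table. Counting all treated patients would fit the accrual wording and give exactly 0.0804 and 0.8033 if 5% and 20% are rates per treated patient. Showing both denominators would also let readers see any exclusions.

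Part of this stands. Treated and evaluable are not reconciled, replacement is permitted but not required, and no all-treated rate is planned. Stating 12 and 21 as evaluable patients and giving the number excluded would read better.

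It does not amount to a defect. The evaluability sentences come immediately before the success rule, so the 21 there is most naturally the counted patients. Section 1.5 is a summary that omits those sentences and sets no competing rule. Section 9.1 supplies the set that Section 11.2 does not repeat. The losses most likely to be informative, early clinical deteriorations, are already counted as failures. The two possible remedies also point in opposite directions, one ending replacement and the other making it compulsory, and each has a price.

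**Conclusion.** No change follows. The text leaves a gap that an analyst would fill sensibly: count to 12 and 21 evaluable patients, replace early consent withdrawals, and state how many were excluded. Handled that way, the stated 0.08 and 0.80 hold for evaluable patients. If withdrawals are not replaced, the rule becomes slightly conservative and power falls to about 0.77 to 0.78 with one loss or 0.73 to 0.75 with two. Discretion over replacement cannot raise type I error above 0.080 on this reading.

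The conclusion rests on taking 5% and 20% as rates among evaluable patients, which is where Section 11.1 places them. The power losses also assume that withdrawal is unrelated to response. If 5% is instead a rate in all treated patients, withdrawers never respond and all are replaced, type I error is 0.091 at 5% withdrawal and 0.103 at 10%. The documents do not establish that combination. Switching to an all-treated rule would override an exclusion stated in two sections and, on the evaluable reading, give up power to correct an error rate that is not inflated. An added all-treated response rate would differ from the evaluable one by about 0.7 points per withdrawal at the success boundary.
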